2.4.5.4 Analyses of vital sign variables

The summary statistics (including number, mean, median, Q1, Q3, SD, minimum and maximum) of all vital signs variables in sitting position (raw values and changes from baseline) will be calculated for each visit or study assessment (baseline, each post-baseline value of the treatment period, last on-treatment, worst on-treatment value and follow-up visit).

Vital signs without position filled in will only be used for the PCSA analysis described below.

The incidence of PCSAs at any time during the TEAE period will be summarized.

2.4.5.5 Analyses of electrocardiogram variables

Not Applicable.

2.4.5.6 Tanner stages measurement

Boys—development of external genitalia, girls—breast development, boys/girls—pubic hair stages as well as a global tanner puberty evaluation (Prepubescent, Pubescent and Postpubescent) will be described using count and percentage.

2.4.5.7 Analyses of other safety endpoints

Binary endpoints defined in [Section 2.1.4.7](#) will be described using count and percentage. Kaplan-Meier curves will be provided for the “Time to” variables. Patient without event will be censored at the end of the treatment period. For the analysis of the time to the first of the two consecutive LDL-C as defined in [Section 2.1.4.7](#), patients without post-baseline LDL-C result or with only one post-baseline LDL-C result will not be included.

2.4.6 Analyses of anti-alirocumab antibodies variables

The following summaries will be performed on the ADA population taking into account all samples regardless of timing in relation to injections.

- ADA results (negative or positive) by time point;

- Neutralizing status (negative or positive) by time point for positive ADA;
- ADA titers using descriptive statistics (median, minimum and maximum) for positive ADA by time point;
- Number (%) of patients with pre-existing ADA and number (%) of patients with treatment-emergent ADA positive response;
- Number (%) of patients with persistent/transient treatment-emergent ADA positive response (for the OLDFI/OLE combined period only);
- Time to onset of treatment-emergent ADA positive response using descriptive statistics, beginning from the first OLDFI IMP administration.
- Number (%) of patients with at least one neutralizing ADA.

2.4.7 Analyses of pharmacokinetic and pharmacodynamic variables

Concentrations of total alirocumab in serum (C_{trough} and C_{Follow-up}), free and total PCSK9 concentrations will be summarized on the PK population by visit using descriptive statistics. C_{trough,av} will be summarized on the PK population using descriptive statistics.

Time profiles for C_{trough} concentration, total and free PCSK9 will be also provided by alirocumab dose group using graphs (mean \pm SE or Median, as appropriate).

Concentrations of total alirocumab in serum and PCSK9 levels might be used for population PK modeling if considered necessary and the results of population PK modeling will be reported separately from the study report.

2.4.8 Analyses of quality of life/health economics variables

Not Applicable.

2.5 DATA HANDLING CONVENTIONS

2.5.1 General conventions

The following formulas will be used for computation of parameters.

Date of birth / Age

In case of partial date of birth, the date of birth will be imputed as follows:

If day only is unknown, it will be replaced by 15 (so estimated date of birth will be 15/ real month / real year). If day and month are unknown, they will be replaced by 30JUN (so estimated date of birth will be 30/ JUN / real year).

The age will be calculated using the imputed date of birth.

At screening, age will be put equal to minimum (age using imputed date of birth; 17.9) for patients without exclusion criterion E01 “Age less than 8 or greater than 17 years at the time of signed informed consent”.

Time from diagnosis of heFH

Time from diagnosis (years) = (Date of informed consent – Date of diagnosis*) / 365.25.

(*): In case the month of diagnosis would be missing, it will be put equal to JANUARY if the year of diagnosis equals the year of informed consent; it will be put equal to JUNE otherwise.

Date of last dose of IMP (for OLDFI and for OLE)

The date of the last injection in the OLDFI period is equal to the last date of administration reported on injection administration case report form page in OLDFI period, or missing if the last administration date is unknown.

The date of the last injection in the OLE period is equal to the last date of administration reported on injection administration case report form page in OLE period, or missing if the last administration date is unknown.

Renal function formulas

eGFR value will be derived using the Schwartz equation:

GFR (mL/min/1.73 m²) = (0.41 × Height in cm) / Creatinine in mg/dL

Lipids variables, laboratory safety variables

For data below the lower limit of quantification (LLOQ) / limit of linearity, half of the lower limit value (ie, LLOQ/2) will be used for quantitative analyses. For data above the upper limit of quantification (ULOQ) / limit of linearity, the upper limit value (ie, ULOQ) will be used for quantitative analyses.

Pharmacokinetic variables

Data below the LLOQ are set to zero.

2.5.2 Data handling conventions for secondary efficacy variables

See [Section 2.1.3](#).

2.5.3 Missing data

For categorical variables, patients with missing data are not included in calculations of percentages unless otherwise specified. When relevant, the number of patients with missing data is presented.

Handling of baseline definition if time of first OLDFI administration or time of assessment at Week 0 visit is missing

If the time of the first OLDFI administration or the time of assessment at Week 0 visit is missing then the baseline value is defined as the last available value obtained before or on the day of the first OLDFI IMP administration.

Handling of computation of treatment duration and compliance if investigational medicinal product first or end of treatment date is missing

If the last or first injection date is missing, the exposure duration and compliance will be left as missing.

Handling of safety and efficacy analysis periods and survival analysis if investigational medicinal product end of treatment date is missing

If the last injection date of OLDFI or OLE period is missing, then this date is imputed to the earliest between

- the last day of the month and year, when applicable or else the 31st of December of the year,
- the date of the end of treatment visit of the period (OLDFI period: Week 8 visit for patients from Cohorts 1 to 3, Week 12 visit for patients from Cohort 4, who completed the OLDFI study treatment period as per protocol, early end of treatment visit for patients who prematurely discontinued the IMP; OLE period: last visit for patients who completed the OLE study treatment period as per protocol, early end of treatment visit for patients who prematurely discontinued the IMP),
- and the date of the last contact,

for the purpose of safety and efficacy analysis period start and/or end.

Handling of medication missing/partial dates

No imputation of medication start/end dates or times will be performed. If a medication date or time is missing or partially missing and it cannot be determined whether it was taken prior or concomitantly, it will be considered a prior, concomitant, and post-treatment medication.

Handling of adverse events with missing or partial date/time of onset, worsening, seriousness

Missing or partial AE dates and times will be imputed so that if the partial AE date/time information does not indicate that the AE started prior to treatment or after the TEAE period, the AE will be classified as treatment-emergent. These data imputations are for categorization purpose only and will not be used in listings. No imputation is planned for date/time of AE resolution.

Handling of adverse events when date and time of first investigational medicinal product administration is missing

When the date and time of the first IMP administration is missing, all AEs that occurred on or

after the day of inclusion will be considered as TEAEs.

When the time of the first OLDFI IMP administration is missing, all AEs that occurred on the day of the first OLDFI IMP administration will be considered as treatment-emergent AEs.

Handling of missing assessment of relationship of adverse events to investigational medicinal product

If the assessment of the relationship to IMP is missing, then the relationship to IMP has to be assumed as possibly related in the frequency tables, but no imputation should be done at the data level.

Handling of potentially clinically significant abnormalities

If a patient has a missing baseline value he will be grouped in the category “normal/missing at baseline.”

For PCSAs with 2 conditions, one based on a change from baseline value and the other on a threshold value or a normal range, with the first condition being missing, the PCSA will be based only on the second condition.

For a PCSA defined on a threshold and/or a normal range, this PCSA will be derived using this threshold if the normal range is missing.

Measurements flagged as invalid by the laboratory will not be summarized or taken into account in the computation of PCSA values.

2.5.4 Windows for time points

Data analyzed by time point (including efficacy, laboratory safety data, vital signs, physical examinations, ADA, PK) will be summarized using the analysis windows given in [Table 3](#) and in [Table 4](#). These analysis windows will be applicable for all analyses, and they are defined to provide more homogeneous data for time point-specific analyses.

Table 3 - Analysis windows definition for OLDFI period

Time point	Targeted study day	Analysis window in study days
Week 4	29	15 to 42
Week 8	57	43 to 63 (for Cohort 4) or 70 (for other cohorts)
Week 10 (for Cohort 4)	71	64 to 77
Week 12 (for Cohort 4)	85	78 to 92
Follow-up (for Cohorts 1 to 3) ^a	Last OLDFI IMP+10 weeks	Last OLDFI IMP+10 weeks ±4 weeks

Study days are calculated from the day of first OLDFI IMP injection, the day of first OLDFI IMP injection being Day 1. For included but not treated patients, Day 1 is the day of inclusion

^a For patients from Cohorts 1 to 3. For patients not entering the open-label extension (OLE) period or who prematurely discontinue the OLE period, only for ADA and PK.

Table 4 - Analysis windows definition for the entire study (OLDFI/OLE combined period)

Time point	Targeted study day	Analysis window in study days
Week 4	29	15 to 42
Week 8	57	43 to 63 (for Cohort 4) or 70 (for other cohorts)
Week 10 (for Cohort 4)	71	64 to 77
Week 12 (for Cohort 4)	85	78 to 92
Week 14 ^a / Week 16 ^b	Number of weeks of the planned visit x 7 +1	Targeted study day-28 to Targeted study day +27
Week 24 ^c / Week 26 ^a / Week 28 ^b	Number of weeks of the planned visit x 7 +1	Targeted study day-28 to Targeted study day +27
Week 36 ^c / Week 38 ^a / Week 40 ^b	Number of weeks of the planned visit x 7 +1	Targeted study day-28 to Targeted study day +27
Week 48 ^c / Week 50 ^a / Week 52 ^b	Number of weeks of the planned visit x 7 +1	Targeted study day-28 to Targeted study day +27
Week 62 ^a / Week 64 ^b	Number of weeks of the planned visit x 7 +1	Targeted study day-28 to Targeted study day +27
Week 74 ^a / Week 76 ^b	Number of weeks of the planned visit x 7 +1	Targeted study day-28 to Targeted study day +27
Week 86 ^a / Week 88 ^b	Number of weeks of the planned visit x 7 +1	Targeted study day-28 to Targeted study day +27
Week 98 ^a / Week 100 ^b	Number of weeks of the planned visit x 7 +1	Targeted study day-28 to Targeted study day +27
Week 110 ^a / Week 112 ^b	Number of weeks of the planned visit x 7 +1	Targeted study day-28 to Targeted study day +27
Week 120 ^a / Week 124 ^b	Number of weeks of the planned visit x 7 +1	Targeted study day-28 to Targeted study day +27
Week 130	911	883 to 938
Follow-up ^d	Last OLE IMP+10 weeks	Last OLE IMP+10 weeks \pm 4 weeks

Study days are calculated from the day of first OLDFI IMP injection, the day of first OLDFI IMP injection being Day 1. For included but not treated patients, Day 1 is the day of inclusion.

a for Cohort 3; the 3 time points will be combined in the analysis.

b for Cohorts 1 & 2; the 3 time points will be combined in the analysis

c for Cohort 4; the 3 time points will be combined in the analysis

d For Cohorts 1 to 3 patients not entering the open-label extension (OLE) period, or who prematurely discontinue the OLE period, only for ADA.

If multiple valid values of a variable exist within an analysis window, the nearest from the targeted study day will be selected. If the difference is a tie, the value after the targeted study day will be used. If multiple valid values of a variable exist within a same day, then the first value of the day will be selected when time is available, else the scheduled visit will be selected.

PK Concentration will be analyzed as Ctrough, Cmax or Cfollow-up following time windows as defined in [Table 5](#). If the date of the previous injection is unknown, the alirocumab concentration will not be considered for the analysis.

Table 5 - Time windows for PK variables definition

PK variables	Time window (D1 = day of previous injection or day of last injection for $C_{\text{follow-up}}$)	
	Q2W regimen	Q4W regimen
Cmax	Day 4 to Day 8	Day 4 to Day 8
Ctrough	Day 9 to Day 22	Day 23 to Day 36
Cfollow-up	Day 23 to last injection + 14 weeks	Day 37 to last injection + 14 weeks

If multiple valid values satisfy the C_{max} , C_{trough} or $C_{\text{follow-up}}$ criteria, the nearest from the targeted study day (ie, Day 15/32 for C_{trough} and Day 70 for $C_{\text{follow-up}}$, Day 1 being the day of previous injection) will be selected. If the difference is a tie, the value after the targeted study day will be used.

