ASSESSMENT SCHEDULE	
MAIN PHASE
 
Screening period:
 
The screening period is up to 6 weeks (+ 1 week), with 1 to 2 visits that are anticipated, depending on the duration of stable LMT dosing and the need for mandatory heFH genetic testing.
 
Patients can be enrolled during this period as soon as eligibility is confirmed.
 
Open-label dose finding treatment period:
 
For Cohorts 1 to 3, visits schedule from entry into the open-label dose finding treatment period: baseline Visit (V2, Week 0) and then every 2 weeks (ie, Weeks 2, 4, 6) until the end of the open-label dose finding period (Week 8). The visits at Week 2 and Week 6 will take place either at the clinical site or patient's home, depending upon local arrangements and preferences of the investigator/patient.
 
For Cohort 4, visits schedule from entry into the open-label dose finding treatment period: baseline, Visit (V2, Week 0), and then every 4 weeks (ie, Weeks 0, 4, and 8) until the end of the open-label dose finding period (Week 12) will take place at the clinical site. Visits at Week 2 and Week 6 will be a phone call and at Week 10 will be at the clinical site.
 
Follow-up period, only for Cohort 1 to Cohort 3:
 
Follow-up visits will take place 6 and 10 weeks after the last alirocumab injection administered during the open-label dose-finding treatment period. This corresponds to Week 12 and Week 16 for Cohorts 1 & 2 or Week 10 and Week 14 for Cohort 3. The Week 10 or Week 12 visit will be conducted through a phone call if there is no safety concern by the investigator.
 
EXTENSION PHASE
 
Open-label extension (OLE) period:
 
After successful completion of Week 16 visit for Cohorts 1 & 2 or Week 14 visit for Cohort 3, patients will be offered entry into an optional OLE period. The first visit of the OLE period will overlap with the final follow-up visit of the main phase. Visits will take place at Week 20, Week 24, Week 28 and then every 12 weeks thereafter for assessments for Cohorts 1 & 2. Visits will take place at Week 18, Week 22, Week 26 and then every 12 weeks thereafter for assessments for Cohort 3. Depending on the clinical supplies and/or alternative contingency plans, more frequent visits such as every 2 weeks (for Cohorts 1 & 2) or every 4 weeks (for Cohort 3) may be required. Visits will continue until visit end of OLE at least 2 or 4 weeks after last alirocumab injection (with a follow-up phone call at least 10 weeks after the last alirocumab administration) before the initiation of the pediatric Phase 3 study in the site where the patient is potentially participating or December 2018, whichever comes first. A follow-up phone call will take place at least 10 weeks after the last IMP of each cohort.
 
All patients enrolled in Cohort 4 who successfully complete the open-label dose-finding treatment period will also be offered either entry into the extension phase at

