a Alirocumab injections may be prepared from vials by the pharmacist (or equivalent) or supplied as prefilled syringes (PFS) depending on availability and additional considerations. If the PFS is available in the extension phase, then patients may either switch from vials to PFS or directly initiate PFS (depending on patient's date of entry into the extension phase). If the PFS is not available in the extension phase, then alirocumab injections prepared from vials will be administered at the site (by the site staff) or at the patient's home or another preferred location contingent upon alternative arrangements being made for such an administration. Depending on the clinical supplies and/or alternative contingency plans, more frequent clinic visits such as every 2 weeks or every 4 weeks may be required for alirocumab administration in addition to the scheduled visits noted in the flowchart.

b The first visit of the OLE period from the extension phase will overlap with the final visit of the follow-up period from the main phase.

- c The end of open-label extension period visit will take place at least 2 or 4 weeks after the last alirocumab administration (with a follow-up phone call at least 10 weeks after the last alirocumab administration) before the initiation of the pediatric Phase 3 study in the site where the patient is potentially participating or December 2018, whichever comes first.
- d In order to enter into the extension phase, the patient must successfully complete the main phase including the 8 week open-label dose finding treatment period.
- e Alirocumab administration will occur every 2 weeks or every 4 weeks. Prior to each alirocumab administration, a local anesthetic may be utilized (as per the Investigator). Alirocumab injections prepared from vials by the pharmacist (or equivalent) will be administered at the clinical site (by the site staff) or at the patient's home or another preferred location contingent upon alternative arrangements being made for such an administration. The last scheduled injection will take place 2 weeks or 4 weeks before the end-of-OLE visit for the Q2W regimen or Q4W regimen, respectively.

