6.2 DURATION OF STUDY PARTICIPATION

6.2.1 Duration of study participation for each patient

Main open-label treatment phase:

For Cohorts 1 to 3, a study duration of approximately 16-23 weeks (screening/run in period: up to 6 [+1] weeks, main open-label treatment period: 8 weeks, follow-up period: 6-8 weeks)

For Cohort 4, a study duration of approximately 14-19 weeks (screening period: up to 6 [+1] weeks, open-label dose-finding treatment period: 12 weeks).

Open-label extension phase:

Patients who enroll in the open-label extension treatment period will continue alirocumab administration until at least 10 weeks before the initiation of the pediatric Phase 3 study in the site where the patient is potentially participating. Therefore, patients who consent to participate in the pediatric phase 3 study could have their last alirocumab injection in the OLE period up to December 2018, depending on timing of site initiation for the phase 3 study planned to be done no later than December 2018. All other patients, enrolled in the OLE period, who decline the participation in the phase 3 study, will have their last alirocumab injection on December 2018. This corresponds to a maximum of approximately 24 months for the first patients enrolled in Cohorts 1 to 3. For Cohort 4, this corresponds to a maximum of approximately 7 months for the first patients enrolled.

For both phases, patients who experience an ongoing Serious Adverse Event (SAE) or an Adverse Event of Special Interest (AESI), at the pre-specified study end-date, should be followed until resolution, stabilization, or death and related data will be collected.

End of study per patient:

If patient does not participate to the open label extension period, then the end of the study is the last on site visit as scheduled by protocol (ie, visit Week 14 or Week 12 (Cohorts 3 & 4, respectively) or Week 16 (Cohorts 1 & 2) or the resolution/stabilization of all SAEs, and AESI, whatever comes last.

If patient participates in the open label extension period, then the end of the study is the last on site visit as scheduled by protocol (ie, visits will continue until visit end of OLE at least 2 or 4 weeks after last alirocumab injection (with a follow-up phone call at least 10 weeks after the last alirocumab administration) before the initiation of the pediatric Phase 3 study in the site where the

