1.3 DETERMINATION OF SAMPLE SIZE

No power sample size calculations were performed for the main phase. A sample size of 10 patients per cohort is empirical and based on the sample size of the Phase 1 studies (R727-CL-904 and R727-CL-1001) conducted in adults. No less than 4 patients with BW < 50 kg and no less than 4 patients with BW ≥ 50 kg will be enrolled in 4 independent cohorts (Cohort 1, Cohort 2,

Cohort 3, and Cohort 4), which will allow the evaluation of the pharmacokinetics/pharmacodynamics (PK/PD) profile and safety of different alirocumab doses/dose regimen in each BW category and to compare with PK/PD profile and safety observed in adult patients.

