1.5 MODIFICATIONS TO THE STATISTICAL SECTION OF THE PROTOCOL

This section summarizes major changes to the protocol statistical section.

The protocol history table below gives the timing, rationale, and key details of major changes to the protocol statistical section.

The first patient was enrolled on 29-Sep-2016 and the first patient enrolled for Cohort 4 is planned on 01-May-2018.

Table 1 - Protocol amendment statistical changes

Amendment Number	Date Approved	Rationale	Description of statistical changes
1	11-Aug-2016	First step analysis was added to select the dose that will be used in the Phase 3 study	Addition of first step analysis
2	11-Dec-2017	Addition of a cohort (Cohort 4) to further evaluate the every 4 weeks (Q4W) dosing regimen at higher doses (150 mg for body weight <50 kg / 300 mg for body weight \geq 50 kg)	Addition of efficacy and safety analyses for Cohort 4 data including efficacy analyses specific to Cohort 4

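### SAP Table 4 leaves holes between extension windows, and no end-of-extension visit can reach the Week 130 window or Cohort 4's Week 48 window, so some end-of-extension values enter no by-time-point summary

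*SAP*

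**What the plan says.** SAP section 2.5.4, Table 4, sets each extension target day as "Number of weeks of the planned visit x 7 +1" and the window as "Targeted study day-28 to Targeted study day +27". Week 130 is written out as Day 911, window 883 to 938. For Cohort 4 the last planned row is Week 48, which shares a line with Weeks 50 and 52 of the other cohorts. The only row tied to the last extension injection is Follow-up, at 10 weeks plus or minus 4 weeks.

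The Protocol synopsis schedules visits at "Week 28 and then every 12 weeks thereafter for assessments for Cohorts 1 & 2", with the matching pattern for Cohort 3. The end-of-extension visit does not follow that grid. It depends on Phase 3 initiation at the site or on December 2018. Protocol section 6.2.1 says that extension patients "who decline the participation in the phase 3 study, will have their last alirocumab injection on December 2018". Protocol section 1.4.1, footnote e, adds: "The last scheduled injection will take place 2 weeks or 4 weeks before the end-of-OLE visit". The Protocol flowcharts nevertheless label Week 130 (Cohorts 1 to 3) and Week 48 (Cohort 4) as end of extension.

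SAP section 1.5 gives the start dates: "The first patient was enrolled on 29-Sep-2016 and the first patient enrolled for Cohort 4 is planned on 01-May-2018". SAP sections 2.1.3 (lipids) and 2.4.5 (safety) state that all measurements, scheduled or not, go to analysis windows. SAP section 2.4.4.2.4 reports combined-period lipids only as observed-data summaries by time point.

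**The concern.** A 56-day window cannot tile an 84-day interval, so some study days belong to no row. That is harmless for visits that follow the grid, but the end-of-extension visit can fall on any study day. So can the lipid and ADA visit after early discontinuation (Protocol section 10.3.4). The two rows meant to receive the end-of-extension visit also appear to lie beyond the date on which dosing stops. At stake are the last on-treatment lipid values of the extension, and the corresponding entries in the by-visit safety and ADA tables.

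**Working it through.** **Inputs.** Window -28 to +27 days; target = 7 x week + 1 (SAP Table 4). First enrolment 29-Sep-2016; first Cohort 4 enrolment planned 01-May-2018 (SAP section 1.5). Last injection by December 2018, taken as 31-Dec-2018 at the latest. End-of-extension visit 14 days (Q2W) or 28 days (Q4W) after the last injection (Protocol section 1.4.1), with a 7-day tolerance (Protocol section 10). Enrolment day is taken as first-injection day.

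**1. Reproduce the plan's figure.** Week 130: 7 x 130 + 1 = 911; 911 - 28 = 883; 911 + 27 = 938. This matches Table 4.

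**2. Coverage.** Width = 28 + 27 + 1 = 56 days; spacing = 12 x 7 = 84 days; hole = 84 - 56 = 28 days.

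| Cohort | Adjacent windows | Uncovered days |
|---|---|---|
| 1-2 | Week 28: 169-224; Week 40: 253-308 | 225-252 (28) |
| 1-2 | Week 112: 757-812; Week 124: 841-896 | 813-840 (28) |
| 3 | Week 110: 743-798; Week 120: 813-868 | 799-812 (14) |
| 3 | Week 120: 813-868; Week 130: 883-938 | 869-882 (14) |
| 4 | Week 12: 78-92; Week 24: 141-196 | 93-140 (48) |
| 4 | Week 24: 141-196; Week 36: 225-280 | 197-224 (28) |

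For Cohorts 1-2, Weeks 124 and 130 overlap on Days 883-896.

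**3. Can the Week 130 window be reached?** 31-Dec-2018 is Day 824 for the first patient. Adding 28 + 7 days gives Day 859, which is 24 days short of Day 883 (28-Feb-2019). Day 859 is also the on-treatment limit for Q4W dosing (824 + 35). Even the Protocol's maximum of about 24 months, taken as 730 days from Day 113 with the longer lag, gives 113 + 730 + 28 + 7 = Day 878.

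**4. Can Cohort 4 reach its Week 48 window?** 31-Dec-2018 is Day 245 for the first planned patient. 245 + 28 + 7 = Day 280, which is 29 days short of Day 309 (05-Mar-2019).

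**5. Examples.** Suppose the first patient is dosed Q2W on schedule from Day 113. The last December 2018 injection is 113 + 50 x 14 = Day 813 (20-Dec-2018), and the end visit is Day 827. With the 7-day tolerance it is Day 820-834, inside the 813-840 hole throughout. The first Cohort 4 patient, on schedule, has the last injection at Week 32 (11-Dec-2018) and the end visit at Week 36, Day 253, inside the Week 36 row.

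**6. Share of end visits in a hole.** On the Q2W grid from Day 197, possible end days in one cycle are 197, 211, 225, 239, 253 and 267; two of six (225, 239) are uncovered. On the Cohort 3 Q4W grid from Day 183 they are 183, 211 and 239; one of three (211) is uncovered. If all offsets are equally likely the share is 1/3. With assumed uniform calendars:

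| Cohort | Assumed enrolment | All stop 31-Dec-2018 | Stops spread uniformly |
|---|---|---|---|
| 1-2 | 29-Sep-2016 to 16-Oct-2017 | 36.0% | 33.4% (Jul-Dec 2018) |
| 3 | same | 34.7% | 33.6% (Jul-Dec 2018) |
| 4 | May-Aug 2018 | 22.8% | 37.1% (Oct-Dec 2018) |

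The October 2017 bound follows from the second amendment (11-Dec-2017), whose rationale says Cohorts 1 to 3 had completed 8 weeks: 11-Dec-2017 minus 56 days is 16-Oct-2017. No scenario puts an end visit in the Week 130 window or, for Cohort 4, in the Week 48 window.

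**The case against.** The strongest reply is that the holes cost little. Several parts of it stand.

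- A reader might infer that a third of the extension data is lost. The documents do not support this. Routine sampling visits have tolerances of 7 or 14 days and always fall inside -28/+27. One third is a share of uncovered days, and the 23-37% applies only to end-of-extension values under assumed stop dates.
- A reader might infer that hormones, vitamins, safety laboratory values and ADA are discarded. They are missing only from by-time-point tables. SAP section 2.4.5 keeps last and worst on-treatment values, and PCSA uses every evaluation in the TEAE period. SAP section 2.4.5.3 counts low hormone and vitamin values over that period. Treatment-emergent ADA runs to the end of the extension (SAP section 2.1.4.8).
- A reader might infer that the whole Week 48 row is empty. Only its Cohort 4 part is; Weeks 50 and 52 share the line. An end visit near study Week 36 placed in the Week 36 row is correctly timed, not mislabelled. The Week 124/130 overlap has no effect if nobody reaches Day 883.
- After the switch to Phase 3 doses, Cohorts 1 to 3 are analysed separately and listings may replace tables (SAP section 2.4). This softens the loss but does not remove it. SAP section 2.5.4 applies the same windows to all analyses, and Cohort 4 has no switch.
- SAP section 2.5.4 sets windows to keep timing homogeneous. That could justify narrow windows, but not alongside the statement that all measurements are assigned to one.
- The Cohort 4 result rests on a planned start date. Reading the Protocol's 7 months as extension time would give 85 + 213 + 28 = Day 326, inside Week 48. That conflicts with December 2018, which allows only 4.3-5.3 months of extension; 7 months fits total treatment (7.0-8.0 months).

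**Conclusion.** The concern holds in a limited form. Table 4 leaves uncovered days, contrary to the SAP's own assignment rule. On the documents' dates no end-of-extension visit reaches the Week 130 window or Cohort 4's part of the Week 48 row. Those visits, and early-discontinuation visits, can therefore enter no by-time-point summary. The loss matters mainly for combined-period lipids, which have no other planned summary, and secondarily for the by-visit laboratory, hormone, vitamin and ADA tables. The Week 8 primary analysis is untouched.

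The window arithmetic needs no assumption. The unreachable rows rest on the two start dates, on first injection at enrolment, and on 31-Dec-2018 as the latest injection. The 23-37% is illustrative and depends on when patients actually stop.

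**What to change.** 1. In place of the fixed Week 130 row and Cohort 4's Week 48 entry, add an End of OLE time point: the last on-treatment extension value, keyed to the visit or the last extension injection and bounded by the existing +21 or +35 day limit. Report the distribution of study day beside it, because exposure durations differ. State whether the value also contributes to its study-week row.
2. Make adjacent extension windows contiguous by splitting at the midpoint between each cohort's planned visits. A uniform -42/+41 will not do: it would start Cohort 3's Week 14 window at Day 57, inside the Week 8 window (43-70), overlap around Weeks 110 and 120, and leave Cohort 4 Days 93-126 uncovered. Keep the present lower bounds for Weeks 14 and 16 (Days 71 and 85), and set boundaries without overlap at Weeks 110, 120 and 124 and after Cohort 4 Week 12.
3. Reconcile the Week 130 and Week 48 end-of-extension labels in the Protocol flowcharts with the December 2018 end date and the stated durations.

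The cost is an edit to one SAP table plus clarification of the flowchart labels, before the final database lock, with no new data. The downside is slightly less homogeneous timing within each row.
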